7.2.2 Serious adverse events (SAEs)

A serious adverse event is any untoward medical occurrence or effect that

- results in death;
- is life threatening (at the time of the event);
- requires hospitalisation or prolongation of existing inpatients' hospitalisation;
- results in persistent or significant disability or incapacity;
- is a congenital anomaly or birth defect; or

- any other important medical event that did not result in any of the outcomes listed above due to TEI but could have been based upon appropriate judgement by the investigator.

In literature, arachnoiditis and 'nervous system disorder' have been described as major complications. However, despite the lack of exact data, these complications are considered to be rare [19].

An elective hospital admission will not be considered as a serious adverse event.

The investigator will report all SAEs to the subsidizing party without undue delay after obtaining knowledge of the events.

The sponsor will report the SAEs through the web portal *ToetsingOnline* to the accredited METC that approved the protocol, within 7 days of first knowledge for SAEs that result in death or are life threatening followed by a period of maximum of 8 days to complete the initial preliminary report. All other SAEs will be reported within a period of maximum 15 days after the sponsor has first knowledge of the serious adverse events.

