7.2 AEs, SAEs and SUSARs

7.2.1 Adverse events (AEs)

Adverse events are defined as any undesirable experience occurring to a subject during the study, whether or not considered related to TEI. All adverse events reported spontaneously by the subject or observed by the investigator or his staff will be recorded.

Adverse events from treatment with TEI are rare. The most common adverse events reported in literature are [19]:

- Transient exacerbation of pain: 2.4%
- Pain at site of injection: 1.1%
- Persisting numbness: 0.33%
- Vasovagal reaction: 0.14%
- Accidental discal puncture: 0-1%
- Accidental dural puncture: 2.3%
- (Post dura puncture) headache: 0.33-1%

This includes also includes leg pain/inability as a result of TEI that:

- requires hospitalisation or prolongation of existing inpatients' hospitalisation;
- results in significant disability or incapacity;

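### The sixth SAE criterion contains a reference to TEI that leaves its scope unclear, above all for control patients

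*Combined protocol and SAP*

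**What the plan says.** Section 7.2.1 defines an adverse event as "any undesirable experience occurring to a subject during the study, whether or not considered related to TEI". Cause and arm play no part. After a list of known TEI complications, the section adds: "This includes also includes leg pain/inability as a result of TEI that" either "requires hospitalisation or prolongation of existing inpatients' hospitalisation" or "results in significant disability or incapacity".

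Section 7.2.2 opens just as broadly: "A serious adverse event is any untoward medical occurrence or effect that" meets one of six criteria. The first five are death, threat to life, hospitalisation, disability and congenital anomaly, and none mentions TEI. The sixth is "any other important medical event that did not result in any of the outcomes listed above due to TEI but could have been", followed by a reference to the investigator's judgement.

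The reporting rule has no filter by arm or cause: "The investigator will report all SAEs to the subsidizing party without undue delay". The ethics committee (METC) is to be told within 7 days of fatal or life-threatening SAEs and within 15 days of all others.

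Three other places bear on the point. Section 3 gives the control arm oral medication and, if needed, physiotherapy, without injection. Section 6.2 states that the trial is open-label. Section 11.2 states that there is no DSMB or safety committee.

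**The concern.** An important-medical-event criterion exists to catch events that stopped short of a listed outcome but might have reached it. It depends more on judgement than the other five criteria, so its wording matters most. Here it carries a reference to the study treatment that the AE definition, the SAE lead-in and the other five criteria do not.

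An investigator who knows the allocation could reasonably conclude that the criterion concerns injections only. A control patient's event of this kind would then go unreported as an SAE, while a comparable event after an injection would be reported. With no DSMB, expedited SAE reporting to the METC is the main continuing outside check that the protocol describes. An unclear trigger for that reporting weakens it.

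**Working it through.** No figure in the plan depends on this point, so the check is textual.

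**Step 1. Where attribution enters.** One of the six criteria mentions TEI and 6 − 1 = 5 do not. Neither the AE definition nor the SAE lead-in imposes a causal condition.

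**Step 2. What the phrase can mean.** In the sixth criterion, 'due to TEI' follows the reference to the outcomes listed above. Three readings are possible.

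- *Causal:* the event could have led to a listed outcome caused by TEI. The criterion is then tied to an injection that control patients do not receive by allocation, and it has no clear use for them.
- *Literal:* the listed outcome did not occur because of TEI. The criterion then covers harm averted by the injection, which makes no sense as a safety rule.
- *Permissive:* the event did not produce a TEI-caused listed outcome. Every control event meets that condition trivially, so the phrase excludes nothing and does no work.

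**Step 3. A test case.** Suppose a patient has a severe reaction to oral analgesics. It is not life-threatening when it occurs and is treated in time, without admission or disability. None of the first five criteria is met, so classification rests on the sixth.

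| Event | Causal | Literal | Permissive |
|---|---|---|---|
| Oral-drug reaction, control arm | not covered | not covered | covered |
| Oral-drug reaction, TEI arm | not covered | not covered | covered |
| Comparable reaction to the injection, TEI arm | covered | not covered | covered |

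The classification changes with the reading. On the causal reading, comparable events are classed by cause. Because only one arm receives TEI by allocation, that also means by arm. No reading gives the phrase a useful function.

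**Step 4. The overlap with 7.2.1.** The hospitalisation item in 7.2.1 has the same wording as the SAE criterion in 7.2.2. The disability items differ: 7.2.1 has "results in significant disability or incapacity" and 7.2.2 has "results in persistent or significant disability or incapacity". The 7.2.2 wording joins its two terms with 'or', so significant disability meets it. Both 7.2.1 items therefore fall within SAE criteria, but 7.2.1 does not say so.

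**Step 5. Whether another section settles it.** Section 7.3 deals with follow-up of events, not classification. The complications parameter in section 6.1.2 concerns events from TEI and gives no rule for control patients.

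**The case against.** The strongest defence is that the wording does not require the event itself to be caused by TEI. On the permissive reading, control events qualify, and the investigator's judgement is there to settle doubtful cases. A severe reaction that threatened life when it occurred would be an SAE under the second criterion in either arm. On this view the phrase is a drafting slip with little practical effect.

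Part of this stands. Exclusion of control patients is one reading and not the only one, and the events at issue are few in kind. But the defence saves the criterion only by giving the phrase no function, which is a reason to delete it. Judgement by an unblinded investigator does not cure a rule whose scope is unclear.

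A reader might infer more than the documents support, in three ways.

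- *That seriousness in general depends on attribution to TEI.* It does not: the lead-in and five of the six criteria are free of attribution.
- *That 7.2.1 and 7.2.2 give conflicting instructions for a TEI patient admitted with worse leg pain.* They do not. Section 7.2.1 says adverse events are recorded, not that they are only recorded, and it exempts nothing from 7.2.2. An unplanned admission is an SAE and must be reported, so a site that follows both sections records and reports it. What is missing is a cross-reference.
- *That a comparison of SAEs between arms will be distorted.* Section 8 plans no such comparison.

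**Conclusion.** The sixth SAE criterion is defective as written and should be corrected. The effect is confined to important medical events that meet none of the other five criteria. For these, classification as an SAE, and so reporting to the METC, can depend on how the phrase is read and on the arm.

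The size cannot be quantified, because the documents give no expected frequency for such events. The planned 142 patients at 1:1 give 142 / 2 = 71 controls. That is the number to whom the unclear rule would apply, not the number expected to be affected. No planned efficacy or between-arm safety analysis changes.

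The conclusion assumes that sites work from the protocol text and that no separate guidance, such as form instructions outside these documents, resolves the scope. The overlap between 7.2.1 and 7.2.2 is a minor clarification that would not merit a point of its own.

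**What to change.** In 7.2.2, delete 'due to TEI' and reword the sixth criterion along these lines: any other important medical event, in either arm and regardless of its relation to TEI, that in the investigator's judgement could have led to one of the outcomes above but did not, for example because of timely intervention.

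In 7.2.1, state that leg pain or inability after TEI that requires hospitalisation or causes significant disability is an SAE and is reported under 7.2.2. Use the same disability wording in both sections.

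If the phrase was meant to capture causality, record relation to TEI as a separate item for each event. The adverse event form is not in the documents, so it may already have one.

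The cost is a short amendment notified to the METC under section 10.3 and, at most, one form field. The downside is possibly a few more SAE reports, including some from the control arm.

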Sponsor	The sponsor is the party that commissions the organisation or performance of the research, for example a pharmaceutical company, academic hospital, scientific organisation or investigator. A party that provides funding for a study but does not commission it is not regarded as the sponsor, but referred to as a subsidising party.
TEI	Transforaminal Epidural Injection
TEIAS	Transforaminal Epidural Injection in Acute Sciatica
VAS	Visual Analogue Scale
WMO	Medical Research Involving Human Subjects Act; in Dutch: Wet Medisch-wetenschappelijk Onderzoek met Mensen

SUMMARY

Rationale: To study (cost) effectiveness of the transforaminal epidural injection with analgesic and anti-inflammatory medication (TEI) in order to relieve the symptoms and to evaluate the intervention as a predictor tool for symptoms of sciatica in the long term.

Objective: To evaluate the percentage of patients that experience satisfactory (long term) decrease in leg pain in the TEI group in comparison to the conservative care group.

Study design: Randomised controlled trial

Study population: Patients that suffer 3-8 weeks from sciatica (Numeric Rating Scale ≥ 6 , on a 10 point scale)

Intervention: transforaminal epidural injection with analgesic and anti-inflammatory medication

Main study parameters/endpoints: the percentage of patients that experience satisfactory decrease (NRS lower than 4) in leg pain after 2, 10 and 21 weeks after randomization in both treatment arms

Nature and extent of the burden and risks associated with participation, benefit and group relatedness: the participants fill in questionnaires at baseline, at 1, 2, 4, 10 and 21 weeks after randomization. Participants will also fill in cost-diaries during this period. TEI as an intervention tool is considered usual care for sciatica patients, though the timing of the injection is not clearly defined. The extent of risk from TEI is comparable to usual care.

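### Section 7.2.2 directs the investigator's SAE reports to the subsidising party, not to the sponsor, who must report them to the METC; unless investigator and sponsor are one party, the written route does not reach the sponsor.

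*Combined protocol and SAP*

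**What the plan says.** The list of abbreviations separates two parties. On the first: "The sponsor is the party that commissions the organisation or performance of the research". Its examples of a sponsor include an academic hospital and an investigator. On the second, a party that funds the study but "does not commission it is not regarded as the sponsor, but referred to as a subsidising party".

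Section 7.2.2 then sets out two steps.

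- Investigator's step: "The investigator will report all SAEs to the subsidizing party without undue delay after obtaining knowledge of the events". No other recipient is named.
- Sponsor's step: "The sponsor will report the SAEs through the web portal" to the METC. For the most serious events the limit is "within 7 days of first knowledge for SAEs that result in death or are life threatening", followed by at most 8 further days to complete the preliminary report. For the rest: "All other SAEs will be reported within a period of maximum 15 days after the sponsor has first knowledge".

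Section 7.1 gives the sponsor the duty to suspend the study when there is sufficient ground to think that subjects' health or safety is at risk. Section 11.2 states that no DSMB or safety committee will be set up.

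**The concern.** The two steps in 7.2.2 do not join. The first ends with the funder, and the second begins with the sponsor. By the protocol's own definition these are different parties, so the text does not say how the sponsor learns of an event.

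The sponsor's two safety duties, expedited reporting to the METC (7.2.2) and suspension (7.1), both depend on that knowledge. With no DSMB or safety committee, expedited reporting carries more weight here than in a trial that has one. The route should also be unambiguous because several parties are involved: GPs manage control-arm care, Spaarne Gasthuis gives the injections, and LUMC researchers process the data. A site that followed the sentence to the letter would have met its stated reporting duty without informing the sponsor.

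**Working it through.** No arithmetic bears on the point beyond the time limits, so the check is a comparison of texts.

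**1. Who receives and who must act**

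| Step | Party named | Source |
|---|---|---|
| Investigator reports an SAE to | Subsidising party | 7.2.2 |
| Subsidising party is | A funder that is not the sponsor | Abbreviations, Sponsor |
| SAE is reported to the METC by | Sponsor | 7.2.2 |
| Study is suspended for safety by | Sponsor | 7.1 |

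The funder cannot be read as the sponsor under another name. A funder that also commissioned the study would be the sponsor by definition and would not be called a subsidising party.

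**2. Is the hand-off stated elsewhere?**

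- 7.2.1 provides for recording adverse events and names no recipient.
- 7.3 covers follow-up of events.
- 10.1 describes data entry into Castor and gives no SAE notification.
- 10.2 defers to a monitoring plan still to be written.
- 10.4 provides a yearly summary to the METC, which includes SAEs but is not expedited.
- 10.5 covers notices of halt and end of study.
- 11.2 covers monitoring after the injection.
- The heading of 7.2 names SUSARs, but no SUSAR procedure follows that could serve as another route.

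None of these tells the investigator or the funder to inform the sponsor.

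**3. What starts each clock**

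| SAE type | Limit | Starts at |
|---|---|---|
| Fatal or life-threatening | 7 days, then at most 8 to complete (7 + 8 = 15 in total) | First knowledge, holder not named; the sponsor is the subject of the sentence |
| All others | 15 days | The sponsor's first knowledge, expressly |

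Both limits therefore have a stated start. For the 7-day limit it could be the investigator's or the sponsor's knowledge. The two readings differ by the hand-off time, which the protocol does not give.

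**4. Two cases**

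- *Investigator and sponsor are different parties.* The written route does not deliver the SAE to the sponsor. The 15-day clock waits on an event that no written step brings about.
- *Investigator and sponsor are the same party.* The sponsor knows as soon as the investigator does, both clocks start then, and the sentence about the funder is only an extra notice.

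Sections 10.4 and 10.5 use the combined forms sponsor/investigator and investigator/sponsor, which favours the second case. Section 7.2.2 gives the two roles separate duties in consecutive paragraphs, which favours the first. The body of the protocol does not settle it.

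**The case against.** The best defence is that investigator and sponsor may be one party. The definition allows it, and 10.4 and 10.5 write the roles jointly, including for the yearly report that covers SAEs. The title pages, which might identify the parties, are not part of the text reviewed, and their absence is no fault of the plan. This objection stands to the extent that the gap is conditional. It does not remove the need to reconcile the text, because 7.2.2 treats the roles as distinct and never says that they coincide.

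A second defence is that 7.2.2 does not say SAEs go only to the funder, and that the sponsor's duty to report presupposes that it is told. That is fair as a guess about practice. It still leaves the hand-off unwritten.

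Two stronger readings are tempting, and the documents support neither.

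- A reader might infer that the 7- and 15-day limits have no defined start. They do: first knowledge in both cases, expressly the sponsor's for the 15-day limit. What is missing is the step that gives the sponsor its knowledge and, for the 7-day limit, the name of the party whose knowledge counts.
- A reader might infer that 7.2.1 downgrades serious events, since it lists hospitalisation and significant disability under adverse events, for "leg pain/inability as a result of TEI that" has those consequences. But 7.2.1 defines adverse events broadly enough to include every serious one. Section 7.2.2 classes hospitalisation and significant disability as serious, excepts only elective admission, and exempts nothing named in 7.2.1. There is no contradiction.

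**Conclusion.** The point holds as an internal inconsistency in the safety text. Section 7.2.2 names as recipient a party that the protocol itself says is not the sponsor, and no other section closes the gap.

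The conclusion rests on one assumption that the documents leave open, namely that investigator and sponsor are not the same party. If they are the same, what remains is a clarification of roles.

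The wording governs the stated route of every SAE. It does not show that any report would in fact be late or lost, and no delay can be derived from the documents. No endpoint, estimate or analysis is affected. It should be corrected because the text concerns safety oversight in a trial without a DSMB or safety committee, and because correction costs almost nothing.

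**What to change.** Amend 7.2.2 in two places.

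1. Replace the subsidising party with the sponsor as recipient of the investigator's SAE reports, adding that the funder may be copied. If investigator and sponsor are the same party, state instead that the investigator acts as sponsor.
2. State whose first knowledge starts the 7-day limit.

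A cross-reference from the hospitalisation and disability items in 7.2.1 to 7.2.2 would help readers but is editorial only.

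The cost is a few words in a protocol amendment notified to the METC. No change to the design, data collection or analysis is needed.

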7.3 Follow-up of adverse events

All AEs will be followed until they have abated, or until a stable situation has been reached. Depending on the event, follow up may require additional tests or medical procedures as indicated, and/or referral to the general physician or a medical specialist.

SAEs need to be reported till end of study within the Netherlands, as defined in the protocol.

8. STATISTICAL ANALYSIS

8.1 Primary study parameter(s)

The study data will be analysed according to the intention-to –treat principle. The mean NRS for leg pain will be compared between the two groups using the unpaired t-test. This will also be done at the 4-week time point.

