There has been extensive research on TEI, but these studies generally include patients with chronic sciatica or a mixed population of patients with acute and chronic symptoms. We performed a systematic review on TEI specifically in the acute phase and it occurred that we could find only one article on the efficacy of epidural injections administered to patients with acute sciatica (<8 weeks of symptoms) [6]. This study, conducted by Spijker et al., randomized 63 patients with a duration of symptoms of at least 2 weeks and a maximum of 4 weeks. Patients were divided over an intervention group (receiving TEI with triamcinolone) and a control group (usual care with non-iv medication). It was demonstrated that

functionality and pain relief in the back were more beneficial in the group that received an injection, but that differences were (too) small. However, the analysis of the effect was averaged over all patients in the treatment group. It is known that there is a group of non-responders after TEI, averaging 33% of patients [5]. If the outcome values of all patients are averaged, no effect will be retrieved, while there could be a clear effect for the responders. In the study of Joswig [5] recruiting 63 patients with radicular pain in the leg, 66% of patients responded well to TEI within hours after the injection and in the first 14 days after injection the VAS leg pain remained around 30 mm on a 100 mm scale. In the non-responders the VAS pain was on average 55 mm and persisted on that level for at least 14 days.

Not only was in Spijker's study no distinction made between responders and non-responders, the injection was lacking a painkilling component, like xylocaine. Moreover, the baseline values for VAS leg pain, VAS back pain and Roland Disability score were lower (better) in the control group, and the group of patients evaluated was relatively small. It appears that there is only little literature on TEI in the acute phase of sciatica and therefore additional research is obligatory.

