4.2 Inclusion criteria

In order to be eligible to participate in this study, a subject must meet all of the following criteria:

- Sciatica;
- Leg pain of 6 or more on a 10 point NRS (Numeric Rating Scale) scale with a duration of >3 and <8 weeks;
- Patient is willing to accept the possible costs for the treatment by the pain physician
- Informed consent.

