4.4 Sample size calculation

We hypothesize that patients in the intervention group will have a mean NRS for leg pain of 4.0 on a 10-point scale at two weeks after treatment with TEI and patients in the control group will have a mean NRS for leg pain of 5.5 two weeks after randomization. A difference of 1.5 points on the NRS scale will be considered clinically relevant [17]. With a standard deviation of 2.6 (according to results of Joswig [18]), a power of 90% and a level of significance of 5% 64 patients are needed per group. This is a total of 128 patients. With a loss to follow-up of 10% we aim to include 142 patients.

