6. METHODS

6.1 Study parameters/endpoints

6.1.1 Main study parameter/endpoint

NRS leg pain: The pain intensity in the leg and the back will be measured with a 10-point horizontal Numeric Rating Scale (NRS), ranging from 0 (no pain) to 10 (worst imaginable pain). During each visit the NRS leg pain and NRS back pain will be scored. The patient is not entitled to see the pain scores indicated during previous visit(s). The NRS scores will be measured at baseline and at 1, 2, 4, 10 and 21 weeks after randomization.

The average score for NRS leg pain at two weeks after injection is compared to the average score for NRS leg pain in the prolonged conservative care group, 2 weeks after randomization. This will be calculated again at 4 weeks after randomization.

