6.2 Randomisation, blinding and treatment allocation

Randomisation will take place using block randomisation in a 1:1 allocation ratio in order to obtain equal study groups. When the patient is enrolled, a randomization envelope will be opened to determine patient allocation. Since this is an open-label randomized controlled trial allocation is not concealed.

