6.3 Study procedures

Patients that are diagnosed by the GP with acute sciatica (3-8 weeks after onset of pain, NRS \geq 6) that meet in- and exclusion criteria will be offered the study. If patients are willing to be randomized, they will be contacted by the study investigator. The study investigator will inform the patients again and checks whether patients have access to e-mail. This is done to make sure that they can fill in the questionnaires online (a web-based database with questionnaires is used for data collection (Castor, LUMC)). The study investigator will ask for informed consent. Randomization will take place. If patients are randomized to the intervention group, they will be sent to the anaesthesiologist and planned for TEI within 4 days after randomization without visiting the neurologist. If patients are randomized to the

control group, they will receive oral pain medication according to the care of the general practitioner.

The patient will be invited to the hospital where baseline data will be gathered and questionnaires will be filled in. During this contact the study investigator will guide the patient through the online questionnaire fill-in procedure to get the patient accustomed with this procedure.

Questionnaires will be filled in after 1, 2, 4, 10 and 21 weeks after randomization for both the control group and TEI group.

If leg pain remains severe after the 2 weeks after randomization primary endpoint, patients can be referred to the neurologist if the general practitioner deems it necessary. Patients can be offered surgery if applicable.

If an MRI is made during the process, MRI data will be gathered as mentioned above.

If a lumbar discectomy is performed, disc tissue will be gathered during surgery and analysed as mentioned above.

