8.2 Secondary study parameter(s)

The absolute decline in NRS leg pain, NRS back pain and ODI and increase in EQ5D from baseline to 2 weeks after randomization will be calculated using t-tests. The same will be done for the baseline to 4 weeks after randomization time point (using t-tests).

Perceived recovery Likert data will be dichotomized (1 and 2 is success, 3-7 is no success) and compared at 2 and 4 weeks after randomization or injection and to 14 and 26 weeks after start of severe leg pain using Chi-square tests.

The 2-week success data will be correlated to the success data after 14 weeks and subsequently for 26 weeks using Chi-square tests to make predictions. Logistic regression analysis will be used to correlate 2-week (and 4-week) success data to the absolute data for NRS leg pain, NRS back pain, ODI, increase in EQ5D at 14 and 26 weeks.

Cost effectiveness analysis:

The economic evaluation will consist of a cost-effectiveness analysis from a healthcare perspective (CEA: costs per extra patient with symptom relieve, i.e. the primary outcome measure) and a cost-utility analysis from a societal perspective (CUA: costs per QALY). Both analyses will be trial-based, using patient reports, with a half-year time horizon. Healthcare use will be valued according to the Dutch guidelines. QALYs will be calculated as the area under the utility curve, estimated using the Dutch tariff for the EQ-5D. As sensitivity analysis, QALYs will also be calculated using the VAS for quality of life (with power transformation). Average costs and patient outcome will be compared according to intention-to-treat, using net-benefit analysis, and using multiple imputation to account for missing data.

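### Baseline leg pain is collected but not used in the primary week-2 t-test; one pre-specified ANCOVA, on a baseline recorded before allocation, would be a low-cost gain

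*Combined protocol and SAP*

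**What the plan says.** Section 8.1 (Primary study parameter(s)) adopts intention-to-treat and gives one test: "The mean NRS for leg pain will be compared between the two groups using the unpaired t-test". It repeats the test at 4 weeks and names no covariate. Section 6.1.1 shows that the covariate will exist: "The NRS scores will be measured at baseline and at 1, 2, 4, 10 and 21 weeks after randomization".

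In treatment comparisons of leg pain, baseline enters only through the secondary t-tests on change in section 8.2: "The absolute decline in NRS leg pain, NRS back pain and ODI and increase in EQ5D from baseline to 2 weeks". Section 8.3 uses baseline clinical data for the MRI analyses, but not to compare the arms. Randomisation is in 1:1 blocks, with no stratification on pain stated (section 6.2).

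Section 4.4 assumes means of 4.0 and 5.5, an SD of 2.6, 90% power and 5% significance, and concludes that "64 patients are needed per group".

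On timing, section 6.2 says: "When the patient is enrolled, a randomization envelope will be opened to determine patient allocation". Section 6.3 describes randomisation and referral first, and then: "The patient will be invited to the hospital where baseline data will be gathered and questionnaires will be filled in". Section 10.1 places baseline data collection at inclusion. No section says that the baseline score comes before the envelope is opened.

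**The concern.** An unadjusted comparison ignores whatever part of the week-2 variance starting pain explains. It also leaves the primary estimate exposed to a chance difference in starting pain between the arms. The protocol recognises this risk: section 1 criticises the earlier acute-sciatica trial because "the baseline values for VAS leg pain, VAS back pain and Roland Disability score were lower (better) in the control group".

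The change-score t-tests in section 8.2 do not fill the gap. They are secondary, they give a second week-2 test of leg pain that may disagree with the first, and at low correlation they have less power than the plain t-test. Low correlation is plausible here because the entry rule, "Leg pain of 6 or more on a 10 point NRS (Numeric Rating Scale) scale", narrows the baseline range. If adjustment is added only after an imbalance has been seen, the choice is open to criticism, so it has to be pre-specified.

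The remedy has one condition. The trial is open-label and the score is self-reported. A baseline score given after the patient knows the allocation may itself be affected by that knowledge, and adjusting for it or subtracting it could introduce bias.

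**Working it through.** **Inputs from the documents.** Difference 1.5, SD 2.6, 5% significance, 90% power and 64 per arm (section 4.4); entry at NRS 6 or more (section 4.2). Sidedness is not stated; two-sided is used because it reproduces the plan's figure.

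**Assumptions.** The correlation r between baseline and week-2 scores is not in the documents: 0.1 to 0.3 is the main range, 0.5 the high case. The baseline SD (SDb) is not given either: 1.0 or 1.5.

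**1. The plan's own figure.** n per arm = 2(1.960 + 1.282)² × 2.6² / 1.5² = 63.1, rounded up to 64 (a one-sided test would give 52). Total 128; 128/0.9 = 142.2 against the stated 142. With the noncentral t on 126 df, power at 64 per arm is 0.8995. The standard error is 2.6 × √(2/64) = 0.460 and the 95% interval half-width is 0.910.

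**2. ANCOVA at the same n.** Residual SD = 2.6√(1 − r²), 125 df. The columns allowing for imbalance multiply the variance by 1 + 1/(2n − 4) = 1 + 1/124, the average cost of random baseline imbalance.

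| r | Residual SD | Power | Power, allowing for imbalance | Half-width, allowing for imbalance |
|---|---|---|---|---|
| 0 | 2.600 | 0.8995 | 0.8971 | 0.913 |
| 0.1 | 2.587 | 0.9023 | 0.9000 | 0.909 |
| 0.2 | 2.547 | 0.9107 | 0.9086 | 0.895 |
| 0.3 | 2.480 | 0.9243 | 0.9224 | 0.871 |
| 0.5 | 2.252 | 0.9624 | 0.9612 | 0.791 |

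A simulation with bivariate normal scores (40,000 trials per r) gave ANCOVA power of 0.897, 0.900, 0.912, 0.923 and 0.961. Type I error was 0.048 to 0.050 for both tests.

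**3. Why the lower range of r is more plausible.** In a normal model with assumed unrestricted baseline means of 5.5 to 7 and SDs of 2.0 to 2.5, keeping only scores from 6 to 10 reduces r from 0.5 to 0.23–0.29, and from 0.7 to 0.38–0.46. The restricted baseline SD is then about 1.0.

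**4. Effect of chance imbalance on the unadjusted estimate.** Shift = z × r × 2.6 × √(2/64) = z × r × 0.460, in either direction.

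| Imbalance | r = 0.1 | r = 0.2 | r = 0.3 | r = 0.5 |
|---|---|---|---|---|
| 1 SE | 0.046 | 0.092 | 0.138 | 0.230 |
| 1.96 SE (extreme) | 0.090 | 0.180 | 0.270 | 0.450 |

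Conditional on the imbalance (normal approximation, r = 0.3), a 1-SE imbalance against the injection arm leaves the t-test with power of P(Z > (0.901 − 1.362)/0.438), about 85%. At 1.96 SE it is about 77%, and the conditional type I error is about 7.9%. At r = 0.1 the corresponding figures are about 89%, 87% and 5.3%.

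**5. Change-score t-test.** SD of change = √(2.6² + SDb² − 2r × 2.6 × SDb). For example, at SDb 1.0 and r = 0.1 it is √(6.76 + 1 − 0.52) = 2.691.

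| SDb | r = 0.1 | r = 0.2 | r = 0.3 | r = 0.5 |
|---|---|---|---|---|
| 1.0 | 0.879 | 0.901 | 0.922 | 0.960 |
| 1.5 | 0.835 | 0.870 | 0.903 | 0.961 |

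It passes the unadjusted test only above r = SDb/(2 × 2.6), which is 0.19 or 0.29.

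**6. Why timing matters.** Suppose knowing the allocation moved the baseline score by 0.5 points in one arm (assumed, for illustration). ANCOVA shifts by 0.5 × r × 2.6/SDb: 0.13, 0.26 and 0.39 for r = 0.1, 0.2 and 0.3 at SDb 1.0, or 0.09, 0.17 and 0.26 at SDb 1.5. The change score shifts by the full 0.5, and the unadjusted t-test by 0.

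**The case against.** The strongest reply is that nothing is broken. The t-test is valid under randomisation, its standard error already includes chance baseline variation, and the trial is adequately powered. In the assumed main range the interval half-width shrinks by only 0.001 to 0.04 points, and a 1-SE shift is small beside a half-width of 0.91 and a target of 1.5. With SDb 1.0 and r = 0.3, the planned change-score test has the same power as ANCOVA (92.2%). The earlier trial had 63 patients and this one plans 142, so large imbalances are less likely. Finally, if baseline really is recorded after allocation, the planned t-test is the safer choice.

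Much of this stands. The gain is probably modest, and overall type I error is not at issue. Two parts do not defeat the point. The long-run validity of the t-test does not help the one trial that happens to be imbalanced, and the change-score test matches ANCOVA only in part of the plausible range. The timing risk is real, but it is a reason to fix the order of steps. It already affects the planned change scores more than it would affect ANCOVA. The order in section 6.3 may be no more than the order of the narrative.

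Two neighbouring matters are separate and adjustment does not settle them. The Summary describes the main endpoint as a percentage below NRS 4, and section 6.1.1 counts the two weeks from injection in one arm and from randomisation in the other.

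**Conclusion.** The point holds as a recommended low-cost improvement. The documents contain no baseline-adjusted comparison of the arms, although the covariate is collected. With r assumed at 0.1 to 0.3, the gain is about 0.1 to 2.3 percentage points of power, together with removal of the linear effect of chance imbalance in leg pain. At r = 0.5 the gain is about 6 points. The worst case, r = 0, costs about 0.2 points. The figures rest on the planned SD of 2.6, 64 analysed per arm and approximately normal scores. The recommendation is conditional on a baseline score recorded before allocation is known, which the plan does not currently guarantee.

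**What to change.** - In section 8.1, name one fixed primary model: ANCOVA of week-2 NRS leg pain on arm and baseline NRS leg pain. Report the unadjusted t-test as a sensitivity analysis.
- In section 8.2, use the same form for week-2 NRS back pain and ODI in place of the change-score t-tests. The documents give no SD or correlation for these outcomes, so no gain is quantified; the aim is one consistent method. For the same reason it could be carried to EQ-5D and the 4-week comparisons.
- State that the baseline score is recorded before the allocation envelope is opened, and align sections 6.3 and 10.1. If the hospital visit does follow randomisation, either reverse the two steps or use as covariate an NRS value recorded at eligibility.

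The cost is a few sentences, one degree of freedom and, at most, a change in the order of two existing steps. No new data are needed and the sample size is unchanged.
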